6.4 Supply of study medication (IMP/Placebo) to local pharmacy

This will be operated by the manufacturer who will supervise the entire pharmaceutical supply chain, including study medication final form (packaging), quality (product release), and logistics (distribution). Distribution to each study site will happen prior to the site initiation.

6.5 Storage of study medication (IMP/Placebo)

The study medication must be stored at room temperature (<30deg C) and not kept in a refrigerator. It will be stored in compliance with local regulations. At all study sites, it will be stored away from other CBD products clearly marked for this study with the PI and EudraCT number on the outer box. It will be stored in a secure area with temperature monitoring and control. In the event of a temperature deviation, pharmacy will report this immediately to the sponsor and not issue medications until cleared by the qualified person.

6.6 Removal of study medication outside of expiry date/ at trial conclusion and destruction

The expiry date will always be reported on the study medication. Study medication outside of the expiry date will not be dispensed and will be destroyed, subject to authorization, on an ongoing basis.

6.7 Withdrawal of Subjects

6.7.1 Withdrawal from study

Category of withdrawal I: As per the Declaration of Helsinki, all participants will have the right to withdraw from the study at any time without giving any reason without any prejudice to their future medical care and will be informed as such before consent. If a participant chooses to withdraw from the study, we will discuss the possibility of withdrawing from the study intervention (treatment) only and to continue their follow-up as closely as possible to the follow-up schedule defined in the protocol. They would be encouraged to not leave the study, even if they no longer wished to take the study medications. However, if a participant expresses the wish to be completely withdrawn from the study, then this view will be respected and implemented by the study team. Although not obliged to give a reason for discontinuation, a reasonable effort will be

made to establish this reason. Data already collected will be kept and included in the final analysis.

6.7.2 Withdrawal from study intervention

Category of withdrawal II: Participants may be withdrawn by the investigator for various reasons including but not limited to the following: protocol violations, inter-current illness, AEs, SAE's, SUSAR's, administrative reasons or other reasons or participation in the RCT affecting their ongoing care. Participants may also be withdrawn by the investigator in case of emergence or worsening of depression, suicidal thoughts or behaviour, or any unusual changes in mood or behaviour, suggesting serious risk to the patient. Patients will be followed up with the same schedule of research assessments as those who continue in the study, till they complete the 6-month follow-up period or till they progress to frank psychosis (whichever is earlier);

Category of withdrawal III: In case of CHR patients experiencing progression to a first episode of psychosis (frank psychosis), they will exit from the study intervention, be deemed as treatment failure, and will only be assessed for safety outcomes after confirming progression to psychosis. In line with established practice, and as used in previous clinical trials in CHR patients ^{12,14} transition to psychosis will be operationally defined using CAARMS ¹. We will carry out complete follow-up of patients who develop frank psychosis during the follow-up period.

Participants who stop treatment early will not be replaced. As an excessive rate of withdrawals can render the study un-interpretable, attempts will be made avoid unnecessary withdrawal of patients.

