4.1.3 Secondary endpoints

Secondary clinical outcomes:

1) Distress associated with psychotic symptoms as measured using the CAARMS ¹ 2) Severity of anxiety symptoms assessed using the Hospital Anxiety and Depression Scale (HADS) ⁶¹ and in the level of global functioning (assessed using the social and role functioning scale) ⁶²

3) Clinical remission, as defined as no longer meeting the criteria for a diagnosis of CHR-APS

4) Total CAARMS score

5) Change (study endpoint minus baseline) in the severity of psychotic symptoms as measured using the CAARMS between the CBD and placebo groups

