6.9 Concomitant Medication

Based on participants' clinical history, concomitant requirement of psychotropic medication is an exclusion criterion for the study. Patients requiring continued treatment with psychotropic medications other than antipsychotic, antidepressant or mood-stabilizer medications during the treatment phase may be withdrawn from the study by the Chief Investigator. Very short-term treatment with rescue medications that have a sedative or calming effect (such as Benzodiazepines) during the study may be allowed. For management of concomitant therapies, please refer to the Investigators Brochure. There is a possibility of pharmacological interactions between CBD and other concomitantly administered drugs as mentioned in the investigator brochure. Throughout the study, investigators may prescribe any other concomitant medications or treatments deemed necessary to provide adequate supportive care. A complete listing of all concomitant medication received during the treatment phase will be recorded in the relevant SDW.

7 Visit assessments

For both the internal pilot and the RCT, the following visit assessments will be performed:

7.1 Screening Visit (Visit window -1): This will take place between one to three weeks prior to the baseline visit. At screening, informed consent will be obtained from those who wish to take part. Consenting patients will then be screened against the study inclusion and exclusion criteria using the CAARMS ¹, and those satisfying the criteria will be recruited by employed or delegated investigators. Safety blood samples (for routine biochemistry and haematology) will be obtained and physical examination and vital signs recorded on all participants screened (i.e. including those who are screen failures/ not randomised for some reason). Also, blood samples for genotyping as well as for cannabinoid measurements will be obtained on all participants screened who consent to it. Consent will be sought to analyse screening data as well as regarding long-term follow up beyond the outcomes of the trial and also to link participants' data to routinely collected data sources such as HES and GP records.

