8.2 Assessment of Efficacy

All the study endpoints for the clinical trial will be compared between the IMP and the placebo groups at study end-point (visit 3/ day 182), adjusting for the baseline.

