12.1 Data collection

Assessment and collection of baseline, outcome and other trial data will be performed as reported in Visit assessments. A detailed description of study instruments is also provided in 8.2 Assessment of Efficacy and 8.3 Procedures for Assessing Efficacy Parameters, they are also included within the Appendix, alongside their scoring algorithms, and coding of missing data.

Whenever possible, follow-up data will be collected independently of study intervention discontinuation. The only occasion in which follow-up data will not be collected is described in 6.6.1 Withdrawal from study Category of withdrawal I (if a participant expresses the wish to be completely withdrawn from the study).

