12.9.6 Missing Data

We anticipate very few participants withdrawing consent and expect those withdrawn to be missing at random. Since linear mixed effect modelling adjusts unbalanced designs to account for patient missing timepoint information, as long as each patient has one post-baseline outcome measure, they would be included in each analysis. However, we will explore patterns of missing data to investigate any evidence against missing at random. If there is evidence against missing at random, we will consider the impact on the analysis and may introduce imputation methods.

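### Section 6.7.2 contradicts itself and section 12.1 on whether efficacy assessments continue after transition to psychosis; under its safety-only rule the day-182 primary score is lost because of a high value on the same instrument

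*Protocol*

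**What the plan says.** Four statements in the protocol bear on what is collected after transition.

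- Section 6.7.2, Category III: a patient who progresses to frank psychosis leaves the study intervention, and will "be deemed as treatment failure, and will only be assessed for safety outcomes after confirming progression to psychosis".
- Section 6.7.2, Category II (withdrawn from the intervention by the investigator): the research schedule continues "till they complete the 6-month follow-up period or till they progress to frank psychosis (whichever is earlier".
- Section 6.7.2, Category III, two sentences after the safety-only rule: "We will carry out complete follow-up of patients who develop frank psychosis during the follow-up period".
- Section 12.1: follow-up is to be collected whether or not study drug is stopped. "The only occasion in which follow-up data will not be collected is described in 6.6.1 Withdrawal from study Category of withdrawal I", that is, complete withdrawal at the participant's wish. (Category I is in 6.7.1, so the cross-reference is also out of date.)

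On the analysis side, section 8.2 has every endpoint "compared between the IMP and the placebo groups at study end-point (visit 3/ day 182), adjusting for the baseline". Section 12.9.5.1 fits a mixed linear model in the ITT population. Section 12.9.6 says the team "expect those withdrawn to be missing at random", keeps anyone with one post-baseline measure, and allows that imputation may be introduced if the data speak against that assumption. The treatment-failure label in 6.7.2 does not reappear in any efficacy analysis the protocol describes.

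**The concern.** Sites could follow either rule in good faith, and the two rules produce different datasets. The difference falls on the primary endpoint. Section 8.3.1 defines that endpoint as severity times frequency, summed over the four CAARMS positive-symptom items. Section 6.7.2 defines transition by CAARMS, and section 8.2.1 says its psychosis threshold rests on severity, frequency and duration. The event that would end efficacy assessment is therefore largely a high value of the endpoint itself.

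If later scores are not collected, the mixed model predicts them from the patient's earlier scores and from patients who stayed under assessment. If CBD changes the risk of transition in either direction, part of its effect on day-182 severity is left out of the comparison. The remission endpoint has a related problem: a patient who is not assessed after transition falls out of the logistic regression instead of counting as not remitted. A separate SAP could say how transitions are analysed, but it could not recover scores that 6.7.2 told sites not to collect.

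**Working it through.** **1. The plan's own figures.** Inputs from section 10.2: effect size 0.4, two-sided t-test at 0.05, 80% power, 32% drop-out. The t-test solution is 99.1 per arm, and the plan uses 100 (power 80.4%). Inflating, 100 / (1 − 0.32) = 147.1, so 148 per arm or 296 in total, which the plan rounds to 300. The sample size reproduces, so this is not a sample-size error. The yardstick for what follows is the 0.4 SD target.

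**2. How many patients.** The protocol gives no 6-month transition rate, so a range is assumed.

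- Section 3.1.1 gives about one-third within 3 years. With a constant hazard (assumption), 1 − (2/3)^(1/6) = 6.5%, and 300 × 0.065 ≈ 20 patients.
- Section 3.1.2 gives 69 events in 672 patients across CBT trials, follow-up length not stated: 10.3%, about 31 of 300.
- Lower end assumed at 3%: 9 of 300.

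**3. Size of the shift when all scores from transition onward are lost.** Shift = (p_placebo − p_CBD) × k, where k is the excess, in SD, of the true score over the model's prediction. With risks of 10.3% and 3% the difference is 0.073. This gives 0.07 SD for k = 1, 0.15 SD for k = 2 and 0.22 SD for k = 3. With equal risks it is zero.

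**4. Simulation check.** A likelihood-based repeated-measures model with 150 per arm, visits at 1, 3 and 6 months, correlation 0.6, a true effect of −0.4 SD before transitions, a jump at transition that persists to 6 months, and 400 runs per scenario (simulation standard error about 0.005). Negative values favour CBD.

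| Transition risk, placebo / CBD | Jump | Full data | Confirming rating kept, later scores lost | Confirming rating also lost |
|---|---|---|---|---|
| 6.5% / 6.5% | 2 SD | −0.41 | −0.41 | −0.41 |
| 10.3% / 3% | 1 SD | −0.47 | −0.45 | −0.40 |
| 10.3% / 3% | 2 SD | −0.55 | −0.50 | −0.40 |
| 3% / 10.3% | 2 SD | −0.26 | −0.31 | −0.41 |

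At a 2 SD jump the shift is 0.05 SD if the confirming rating is in the model (0.55 − 0.50) and 0.15 SD if it is not (0.55 − 0.40). When CBD has fewer transitions, its benefit is understated. When it has more, the benefit is overstated by the same amounts (0.31 − 0.26 and 0.41 − 0.26).

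**5. Remission.** If a fraction p of patients are unassessed non-remitters, the observed proportion is the true one divided by (1 − p). For p = 3%, 1 / 0.97 = 1.03. For p = 69/672, 1 / 0.897 = 1.11. Observed remission is inflated by about 3% to 11% in relative terms. This is an upper figure for each p, because a patient whose transition is confirmed at visit 3 is assessed there.

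**The case against.** The best defence is that the worst score is not lost. The safety-only rule starts after progression is confirmed, confirmation is on CAARMS, and section 12.9.6 keeps anyone with one post-baseline measure. If the confirming rating is in the model, later missingness depends on an observed value, which is compatible with missing at random. Much of this stands: in the simulation it recovers about two-thirds of the shift, and the 0.05 SD that remains depends on the jump persisting in full to day 182. But the flowchart in section 4.3 schedules post-baseline CAARMS only at weeks 4, 13 and 26, and nothing says that a rating made between visits becomes analysis data.

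A second defence is that handling of transitions belongs in the SAP. That is fair for the analysis method, and the unused treatment-failure label alone would be no finding. It does not answer the contradiction about collection.

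Three stronger readings are tempting and not supported.

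- From section 4.1.3 ("Clinical remission, as defined as no longer meeting the criteria for a diagnosis of CHR-APS") a reader might infer that frank psychosis would count as remission. Section 8.3.1 rules this out for anyone assessed, since remission needs low scores on all four positive items and a low frequency score. Only the denominator problem remains.
- A reader might infer that up to 40% of the target effect is at stake (0.08 × 2 = 0.16 SD against 0.4). That needs an assumed 8-point risk difference, larger than the whole 6.5% risk implied by one-third in 3 years, together with a 2 SD gap and loss of the confirming rating. Section 3.1.2 also reports no demonstrated effect of existing treatments on transition at 6 or 12 months. The 0.15 SD case above rests on a similar contrast, so it illustrates an unfavourable case and is not an expectation.
- A reader might want to rewrite sections 6.9 ("may be withdrawn from the study by the Chief Investigator") and 8.4.1 (withdrawal after a positive pregnancy test). Those concern other situations, and this point gives no basis for choosing their withdrawal rules.

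**Conclusion.** The contradiction is real: 6.7.2 gives two opposite instructions for the same patients, and its safety-only rule and the Category II cut-off both conflict with 12.1. Reading the promised complete follow-up as safety follow-up does not rescue the text, because 12.1 allows data loss only on Category I withdrawal.

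The consequence is conditional. It arises only under the safety-only reading, and it biases the treatment difference only if transition risks differ between arms; the direction cannot be fixed in advance. With assumed risks of 3% and 10.3% and a 2 SD jump, the shift is about 0.05 SD with the confirming rating in the model and about 0.15 SD without it, against the 0.4 SD target. Observed remission would be about 3% to 11% too high in relative terms for transition rates of 3% to 10.3%. The transition rates, jump, persistence and correlation are assumptions; the protocol supplies none of them.

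**What to change.** Reconcile 6.7.2 with 12.1 on data collection only, leaving the rule on leaving study intervention as it is:

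- In Categories II and III, state that the scheduled efficacy assessments (CAARMS, HADS, social and role functioning) continue to day 182 after transition, unless the participant withdraws consent for follow-up. Remove the safety-only wording and the cut-off of research assessments at progression.
- Record the CAARMS rating that confirms transition as study data, and state that it enters the primary model.
- Add one sensitivity analysis of the primary outcome that treats transition as treatment failure.
- Count transition as non-remission, with all patients in the denominator.
- Correct the cross-reference in 12.1 to 6.7.1.
- Sections 6.9 and 8.4.1 must also be reconciled with 12.1 on whether data collection continues. No change to their clinical rules is proposed here.

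The cost is protocol wording, one extra analysis, and some research interviews with patients after transition, at visits already scheduled. Day-182 scores after transition will also reflect the care given afterwards; the sensitivity analysis is there to show how much that matters.

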6.8 Subject Compliance

Compliance with CBD treatment will be assessed using pill-counts at visits 2, 3 and 4. Patients will be defined as complying in the presence of a pill count greater than 50% the expected number taken.

Furthermore, before the end of the study we will document a secondary measure of compliance by carrying out assay of CBD levels in blood at visits 1-4 in both arms of the study.

Patients who are defined as non-complying with the medication will be coded as protocol deviators.

6.9 Concomitant Medication

Based on participants' clinical history, concomitant requirement of psychotropic medication is an exclusion criterion for the study. Patients requiring continued treatment with psychotropic medications other than antipsychotic, antidepressant or mood-stabilizer medications during the treatment phase may be withdrawn from the study by the Chief Investigator. Very short-term treatment with rescue medications that have a sedative or calming effect (such as Benzodiazepines) during the study may be allowed. For management of concomitant therapies, please refer to the Investigators Brochure. There is a possibility of pharmacological interactions between CBD and other concomitantly administered drugs as mentioned in the investigator brochure. Throughout the study, investigators may prescribe any other concomitant medications or treatments deemed necessary to provide adequate supportive care. A complete listing of all concomitant medication received during the treatment phase will be recorded in the relevant SDW.

7 Visit assessments

For both the internal pilot and the RCT, the following visit assessments will be performed:

7.1 Screening Visit (Visit window -1): This will take place between one to three weeks prior to the baseline visit. At screening, informed consent will be obtained from those who wish to take part. Consenting patients will then be screened against the study inclusion and exclusion criteria using the CAARMS ¹, and those satisfying the criteria will be recruited by employed or delegated investigators. Safety blood samples (for routine biochemistry and haematology) will be obtained and physical examination and vital signs recorded on all participants screened (i.e. including those who are screen failures/ not randomised for some reason). Also, blood samples for genotyping as well as for cannabinoid measurements will be obtained on all participants screened who consent to it. Consent will be sought to analyse screening data as well as regarding long-term follow up beyond the outcomes of the trial and also to link participants' data to routinely collected data sources such as HES and GP records.

7.2 Baseline Visit (Randomisation, on Day 0): Following satisfactory completion of screening, patients will be randomised to one of the treatment arms in a double-blind manner. Before randomisation baseline measures (CAARMS and HADS including alcohol and drug use (in particular cannabis)⁶⁸⁻⁷⁰), physical examination and blood samples for cannabinoid levels and for Cannabidiol will be acquired. The participant will be randomised and study drugs dispensed from the local hub pharmacy. Side effects will also be assessed, by using the UKU side-effect rating scale ⁶³.

7.3 Month One Visit (Visit window 1, at approximately day 28): This visit will involve only clinical assessments, assessment of alcohol and drug use (in particular cannabis), blood sampling, monitoring of compliance, side effects, AEs, and dispensing of study drugs.

7.4 Month three Visit (Visit window 2, at approximately Day 91) and Month Six Visit (Visit window 3, at approximately Day 182): These visits will involve only clinical assessments, assessment of alcohol and drug use (in particular cannabis), blood sampling, monitoring of compliance and side effects as well as AEs. Study drugs will be dispensed as well on visit 3.

7.5 Month Seven Final safety visit (Visit window 4, at approximately Day 212): Only AEs will be recorded at this visit, via review of medical records.

7.6 Laboratory Tests

Clinical Laboratory measures: Bloods for Haematology (Full blood count and Haemoglobin) and Biochemistry (Urea & Electrolytes, liver function test, lipid profile). All blood tests will be carried out at each study site as per their standard procedure. Blood results will be printed and filed as source in the patient SDW.

Genotyping and cannabinoid measures: Blood samples for these measures will be carried out at each study site and shipped to the London site where they will be stored and analysed. Genomic and proteomic samples will be stored for use in future ethically approved research.

8 Outcomes

8.1 Assessment of Feasibility

At 12 months following start of the first patient recruited we will assess the feasibility of conducting the study through an internal pilot where we will assess the following outcomes:

- To have screened 410 eligible patients.
- To have consented a minimum of 20% of the eligible patients.
- To have randomised a minimum of 60 patients.

• To have completed six-month follow-up from at least 70% patients (who require follow-up).

We will proceed to the full study based on satisfying the following go/no go criteria:

• To have screened 410 eligible patients within 12 months of the start of patient recruitment.

• To have consented a minimum of 20% of the eligible patients within 12 months of the start of patient recruitment (e.g. at least 82 out of 410).

• To have randomised a minimum of 60 patients within 12 months of the start of patient recruitment. (By the Go/ No Go time-point, we anticipate 20 of the randomised patients to have completed the 6-month follow-up end-point).

• To have completed six-month follow-up of at least 70% of the randomised patients who are expected to have completed their 6-month follow-up within 12 months of the start of patient recruitment (e.g. 14 out of 20 randomised patients that are eligible for their follow-up and have reached Month 7).

